**Table 12-6 On-treatment deaths by preferred term (Safety Set)**

Primary reason (preferred term)	Cohort A	Cohort B	All subjects
	N=xx	N=xx	N=xx
	n (%)	n (%)	n (%)
Number of subjects who died	xx (xx.x)	xx (xx.x)	xx (xx.x)

Disease Progression	xx (xx.x)	xx (xx.x)	xx (xx.x)
Other	xx (xx.x)	xx (xx.x)	xx (xx.x)
Cardiac tamponade	xx (xx.x)	xx (xx.x)	xx (xx.x)
Breast cancer	xx (xx.x)	xx (xx.x)	xx (xx.x)
Prostate cancer	xx (xx.x)	xx (xx.x)	xx (xx.x)

MedDRA version <xx.x>.

Source: Table 14.3.1-1.3

**Table 12-7 Serious adverse events, regardless of study drug relationship by preferred term, maximum severity and treatment group (Safety Set)**

Primary system organ class	Cohort A (N=xxx)		Cohort B (N=xxx)		All Subjects (N=xxx)	
	All grades	Grade 5	All grades	Grade 5	All grades	Grade 5
	n (%)	n (%)	n (%)	n (%)	n (%)	n (%)
-Total	xx (xx.x)	xx (xx.x)	xx (xx.x)	xx (xx.x)	xx (xx.x)	xx (xx.x)
Cardiac disorders	xx (xx.x)	xx (xx.x)	xx (xx.x)	xx (xx.x)	xx (xx.x)	xx (xx.x)
xxxxxxxxxxxxxxxxxxxxxxxx	xx (xx.x)	xx (xx.x)	xx (xx.x)	xx (xx.x)	xx (xx.x)	xx (xx.x)
xxxxxxxxxxxxxxxxxxxxxxxx	xx (xx.x)	xx (xx.x)	xx (xx.x)	xx (xx.x)	xx (xx.x)	xx (xx.x)
xxxxxxxxxxxxxxxxxxxxxxxx	xx (xx.x)	xx (xx.x)	xx (xx.x)	xx (xx.x)	xx (xx.x)	xx (xx.x)
xxxxxxxxxxxxxxxxxxxxxxxx	xx (xx.x)	xx (xx.x)	xx (xx.x)	xx (xx.x)	xx (xx.x)	xx (xx.x)
xxxxxxxxxxxxxxxxxxxxxxxx	xx (xx.x)	xx (xx.x)	xx (xx.x)	xx (xx.x)	xx (xx.x)	xx (xx.x)
xxxxxxxxxxxxxxxxxxxxxxxx	xx (xx.x)	xx (xx.x)	xx (xx.x)	xx (xx.x)	xx (xx.x)	xx (xx.x)

- Primary system organ class is sorted in descending frequency, as reported in "All Subjects" and "All grades".
- A subject with multiple occurrences of an AE is counted only once in the AE category.
- A subject with multiple adverse events is counted only once in the total row.
- MedDRA version <xx.x> has been used for the reporting.

Source: Table 14.3.1-1.5

**Table 12-8 Adverse events leading to study drug discontinuation, regardless of study drug relationship by preferred term, maximum severity and treatment group (Safety Set)**

Please use the same shell as [Table 12-3](#)

Source: Table 14.3.1-1.6

**Table 12-9 Non-serious adverse events (threshold = x%) by system organ class and preferred term (Safety Set)**

Please use the same shell as [Table 14.3.1-1.8](#)

Source: Table 14.3.1-1.8

## **Shells and specifications for Sections 14 and 16 of the CSR**

### **Section 14 Tables, figures and graphs referred to but not included in the text**

#### **Section 14.1 Demographic data**

**Table 14.1-1.1 Subject disposition (FAS)**

	Cohort A N=xx n (%)	Cohort B N=xx n (%)	All subjects N=xx n (%)
Subject treated	xx (xx.x)	xx (xx.x)	xx (xx.x)
Completed scheduled treatment	xx (xx.x)	xx (xx.x)	xx (xx.x)
Treatment ongoing	xx (xx.x)	xx (xx.x)	xx (xx.x)
Discontinued from treatment	xx (xx.x)	xx (xx.x)	xx (xx.x)
Reason for discontinuation			
Reason 1	xx (xx.x)	xx (xx.x)	xx (xx.x)
Reason 2	xx (xx.x)	xx (xx.x)	xx (xx.x)
Reason 3	xx (xx.x)	xx (xx.x)	xx (xx.x)
Completion Status			
Completed study	xx (xx.x)	xx (xx.x)	xx (xx.x)
Discontinued from study	xx (xx.x)	xx (xx.x)	xx (xx.x)
Reason for discontinuation			
Reason 1	xx (xx.x)	xx (xx.x)	xx (xx.x)
Reason 2	xx (xx.x)	xx (xx.x)	xx (xx.x)
Reason 3	xx (xx.x)	xx (xx.x)	xx (xx.x)
Reason 4	xx (xx.x)	xx (xx.x)	xx (xx.x)

- Percentage is based on N
- Reason for end of study is from CRF end of study page

**Table 14.1-2.1 Analysis set (FAS)**

Analysis set	Cohort A N=xx n (%)	Cohort B N=xx n (%)	All subjects N=xx n (%)
Full analysis set (FAS)	xx (xx.x)	xx (xx.x)	xx (xx.x)
Safety set	xx (xx.x)	xx (xx.x)	xx (xx.x)
Pharmacokinetic analysis set	xx (xx.x)	xx (xx.x)	xx (xx.x)

- N is the number of subjects in FAS.
- Full analysis set includes all subjects who received at least one dose of study
- Safety set includes all subjects who received at least one dose of study medication
- The Pharmacokinetic analysis set includes all subjects who provide at least one evaluable PK concentration.

**Table 14.1-3.1 Demographics (FAS)**

Demographic Variable	Cohort A N=xx	Cohort B N=xx	All subjects N=xx
Age (years)			
n	xx	xx	xx
Mean (SD)	xx.x (x.xx)	xx.x (x.xx)	xx.x (x.xx)
Median	xx.x	xx.x	xx.x
Min - Max	xx.x - xx.x	xx.x - xx.x	xx.x - xx.x
Age category (years)-n (%)			
<65	xx (xx.x)	xx (xx.x)	xx (xx.x)
>= 65	xx (xx.x)	xx (xx.x)	xx (xx.x)
Missing	xx (xx.x)	xx (xx.x)	xx (xx.x)
Sex-n (%)			
Female	xx (xx.x)	xx (xx.x)	xx (xx.x)
Male	xx (xx.x)	xx (xx.x)	xx (xx.x)
Missing	xx (xx.x)	xx (xx.x)	xx (xx.x)
Race-n (%)			
African American/African Heritage	xx (xx.x)	xx (xx.x)	xx (xx.x)
American Indian or Alaskan Native	xx (xx.x)	xx (xx.x)	xx (xx.x)
Asian - Central/South Asian Heritage	xx (xx.x)	xx (xx.x)	xx (xx.x)
East Asian Heritage	xx (xx.x)	xx (xx.x)	xx (xx.x)
Asian - Japanese Heritage	xx (xx.x)	xx (xx.x)	xx (xx.x)
Asian - South East Asian Heritage	xx (xx.x)	xx (xx.x)	xx (xx.x)
Native Hawaiian or Other Pacific Islander	xx (xx.x)	xx (xx.x)	xx (xx.x)
White - Arabic/North	xx (xx.x)	xx (xx.x)	xx (xx.x)

African Heritage			
White -			
White/Caucasian/European Heritage	xx (xx.x)	xx (xx.x)	xx (xx.x)
Missing	xx (xx.x)	xx (xx.x)	xx (xx.x)
Ethnicity-n (%)			
Hispanic/Latino	xx (xx.x)	xx (xx.x)	xx (xx.x)
Not Hispanic/Latino	xx (xx.x)	xx (xx.x)	xx (xx.x)
Missing	xx (xx.x)	xx (xx.x)	xx (xx.x)
ECOG Performance Status-n (%)			
0	xx (xx.x)	xx (xx.x)	xx (xx.x)
1	xx (xx.x)	xx (xx.x)	xx (xx.x)
2	xx (xx.x)	xx (xx.x)	xx (xx.x)
3	xx (xx.x)	xx (xx.x)	xx (xx.x)
4	xx (xx.x)	xx (xx.x)	xx (xx.x)
Missing	xx (xx.x)	xx (xx.x)	xx (xx.x)
Weight (kg)			
n	xx	xx	xx
Mean (SD)	xx.x(x.xx)	xx.x(x.xx)	xx.x(x.xx)
Median	xx.x	xx.x	xx.x
Min - Max	xx.x - xx.x	xx.x - xx.x	xx.x - xx.x
Height (cm)			
n	xx	xx	xx
Mean (SD)	xx.x(x.xx)	xx.x(x.xx)	xx.x(x.xx)
Median	xx.x	xx.x	xx.x
Min - Max	xx.x - xx.x	xx.x - xx.x	xx.x - xx.x
Body Mass Index (BMI) (kg/m  ) #			
n	xx	xx	xx
Mean (SD)	xx.x(x.xx)	xx.x(x.xx)	xx.x(x.xx)
Median	xx.x	xx.x	xx.x
Min - Max	xx.x - xx.x	xx.x - xx.x	xx.x - xx.x

## **Section 14.2 Efficacy and other non-safety data (e.g. PK, PK/PD, Health Econ., QoL)**

## **Section 14.3 Safety data**

**Table 14.3-1.1 Duration of exposure to study treatment (Safety Set)**

	Cohort A	Cohort B	All Subjects
Duration of exposure categories (weeks)-n (%)			
< 1	xx (xx.x)	xx (xx.x)	xx (xx.x)
1 - <4	xx (xx.x)	xx (xx.x)	xx (xx.x)
4 - <8	xx (xx.x)	xx (xx.x)	xx (xx.x)
8 - <12	xx (xx.x)	xx (xx.x)	xx (xx.x)
12 - <24	xx (xx.x)	xx (xx.x)	xx (xx.x)
24 - <48	xx (xx.x)	xx (xx.x)	xx (xx.x)
48 - <60	xx (xx.x)	xx (xx.x)	xx (xx.x)
>=60	xx (xx.x)	xx (xx.x)	xx (xx.x)
Duration of exposure (months)			
Mean (SD)	xx.x (x.xx)	xx.x (x.xx)	xx.x (x.xx)
Median	xx.x	xx.x	xx.x
Q1-Q3	xx.x-xx.x	xx.x-xx.x	xx.x-xx.x
Min - Max	xx.x-xx.x	xx.x-xx.x	xx.x-xx.x

- A subject is counted in only one duration range.

**Programming Note:**

1. Duration of exposure in days = Last dosing date – First dosing date + 1

**Table 14.3-1.2 Summary statistics of exposure of study treatment by compound (Safety Set)**

Exposure variable	Dabrafenib N=xx	Trametinib N=xx
Exposure categories (weeks) -n (%)		
< 1	xx (xx.x)	xx (xx.x)
1 - <4	xx (xx.x)	xx (xx.x)
4 - <8	xx (xx.x)	xx (xx.x)
8 - <12	xx (xx.x)	xx (xx.x)
12 - <24	xx (xx.x)	xx (xx.x)
24 - <48	xx (xx.x)	xx (xx.x)
48 - <60	xx (xx.x)	xx (xx.x)
>=60	xx (xx.x)	xx (xx.x)
Duration of exposure (months)		
Mean (SD)	xx.x (x.xx)	xx.x (x.xx)
Median	xx.x	xx.x
Q1-Q3	xx.x-xx.x	xx.x-xx.x
Min - Max	xx.x-xx.x	xx.x-xx.x
Cumulative dose (mg)		
Mean (SD)	xx.x (x.xx)	xx.x (x.xx)
Median	xx.x	xx.x
Q1-Q3	xx.x-xx.x	xx.x-xx.x
Min - Max	xx.x-xx.x	xx.x-xx.x

**Section 14.3.1 Displays of adverse events**

**Table 14.3.1-1.1 Adverse events, regardless of study drug relationship by primary system organ class, preferred term, maximum severity and treatment group (Safety Set)**

Primary system organ class Preferred term	Cohort A (N=xxx)		Cohort B (N=xxx)		All Subjects (N=xxx)	
	All grades n (%)	Grade ≥3 n (%)	All grades n (%)	Grade ≥3 n (%)	All grades n (%)	Grade ≥3 n (%)
Number of subjects with at least one event	xx (xx.x)	xx (xx.x)	xx (xx.x)	xx (xx.x)	xx (xx.x)	xx (xx.x)
Cardiac disorders						
-Total	xx (xx.x)	xx (xx.x)	xx (xx.x)	xx (xx.x)	xx (xx.x)	xx (xx.x)
Angina pectoris	xx (xx.x)	xx (xx.x)	xx (xx.x)	xx (xx.x)	xx (xx.x)	xx (xx.x)
Oedema NOS	xx (xx.x)	xx (xx.x)	xx (xx.x)	xx (xx.x)	xx (xx.x)	xx (xx.x)
Oedema lower limb	xx (xx.x)	xx (xx.x)	xx (xx.x)	xx (xx.x)	xx (xx.x)	xx (xx.x)
Bradycardia NOS	xx (xx.x)	xx (xx.x)	xx (xx.x)	xx (xx.x)	xx (xx.x)	xx (xx.x)
Oedema peripheral	xx (xx.x)	xx (xx.x)	xx (xx.x)	xx (xx.x)	xx (xx.x)	xx (xx.x)
Sinus bradycardia	xx (xx.x)	xx (xx.x)	xx (xx.x)	xx (xx.x)	xx (xx.x)	xx (xx.x)
Tachycardia NOS	xx (xx.x)	xx (xx.x)	xx (xx.x)	xx (xx.x)	xx (xx.x)	xx (xx.x)

Numbers (n) represent counts of subjects.

A subject with multiple severity grades for an AE is only counted under the maximum grade.

MedDRA version <xx.x>, CTCAE version <x.xx>.

*Programming Note:*

*Sort SOC by alphabetical order, PTs by descending frequency in Investigational drug column of highest relevance and subgroup (e.g. subgroup with highest N).*

**Table 14.3.1-1.2 Adverse events, suspected to be study drug related by primary system organ class, preferred term, maximum severity and treatment group (Safety Set)**

Please use the same shell as [Table 14.3.1-1.1](#)

**Table 14.3.1-1.3 On-treatment deaths, by system organ class and preferred term (Safety set)**

Primary system organ class Primary reason (preferred term)	Cohort A N=xx n (%)	Cohort B N=xx n (%)	All subjects N=xx n (%)
Number of subjects who died	xx (xx.x)	xx (xx.x)	xx (xx.x)
Disease Progression	xx (xx.x)	xx (xx.x)	xx (xx.x)
Other	xx (xx.x)	xx (xx.x)	xx (xx.x)
Cardiac disorders	xx (xx.x)	xx (xx.x)	xx (xx.x)
Cardiac tamponade	xx (xx.x)	xx (xx.x)	xx (xx.x)
Neoplasms Benign, Malignant And Unspecified (Incl Cysts And Polyps)	xx (xx.x)	xx (xx.x)	xx (xx.x)
Breast cancer	xx (xx.x)	xx (xx.x)	xx (xx.x)
Prostate cancer	xx (xx.x)	xx (xx.x)	xx (xx.x)
Respiratory, Thoracic And Mediastinal Disorders	xx (xx.x)	xx (xx.x)	xx (xx.x)
Pneumonia	xx (xx.x)	xx (xx.x)	xx (xx.x)
Pneumonia aspiration	xx (xx.x)	xx (xx.x)	xx (xx.x)
MedDRA version <xx.x>.			

**Table 14.3.1-1.4 All deaths, by system organ class and preferred term (Safety set)**

Primary system organ class Primary reason (preferred term)	Cohort A N=xx n (%)	Cohort B N=xx n (%)	All subjects N=xx n (%)
Number of subjects who died	xx (xx.x)	xx (xx.x)	xx (xx.x)
Disease Progression	xx (xx.x)	xx (xx.x)	xx (xx.x)
Other	xx (xx.x)	xx (xx.x)	xx (xx.x)
Cardiac disorders	xx (xx.x)	xx (xx.x)	xx (xx.x)
Cardiac tamponade	xx (xx.x)	xx (xx.x)	xx (xx.x)
Neoplasms Benign, Malignant And Unspecified (Incl Cysts And Polyps)	xx (xx.x)	xx (xx.x)	xx (xx.x)
Breast cancer	xx (xx.x)	xx (xx.x)	xx (xx.x)
Prostate cancer	xx (xx.x)	xx (xx.x)	xx (xx.x)
Respiratory, Thoracic And Mediastinal Disorders	xx (xx.x)	xx (xx.x)	xx (xx.x)
Pneumonia	xx (xx.x)	xx (xx.x)	xx (xx.x)
Pneumonia aspiration	xx (xx.x)	xx (xx.x)	xx (xx.x)

Includes both on-treatment deaths, and those that occurred more than 30 days after last treatment.  
MedDRA version <xx.x>.

Programming Note:

1. Deaths recorded on EOT page or within 30 days of last study treatment.

**Table 14.3.1-1.5 Serious adverse events, regardless of study drug relationship by primary system organ class, preferred term, maximum severity and treatment group (Safety Set)**

Primary system organ class Preferred term	Cohort A (N=xxx)		Cohort B (N=xxx)		All Subjects (N=xxx)	
	All grades n (%)	Grade 5 n (%)	All grades n (%)	Grade 5 n (%)	All grades n (%)	Grade 5 n (%)
Number of subjects with at least one event	xx (xx.x)	xx (xx.x)	xx (xx.x)	xx (xx.x)	xx (xx.x)	xx (xx.x)
Cardiac disorders						
-Total	xx (xx.x)	xx (xx.x)	xx (xx.x)	xx (xx.x)	xx (xx.x)	xx (xx.x)
Angina pectoris	xx (xx.x)	xx (xx.x)	xx (xx.x)	xx (xx.x)	xx (xx.x)	xx (xx.x)
Oedema NOS	xx (xx.x)	xx (xx.x)	xx (xx.x)	xx (xx.x)	xx (xx.x)	xx (xx.x)
Oedema lower limb	xx (xx.x)	xx (xx.x)	xx (xx.x)	xx (xx.x)	xx (xx.x)	xx (xx.x)
Bradycardia NOS	xx (xx.x)	xx (xx.x)	xx (xx.x)	xx (xx.x)	xx (xx.x)	xx (xx.x)
Oedema peripheral	xx (xx.x)	xx (xx.x)	xx (xx.x)	xx (xx.x)	xx (xx.x)	xx (xx.x)
Sinus bradycardia	xx (xx.x)	xx (xx.x)	xx (xx.x)	xx (xx.x)	xx (xx.x)	xx (xx.x)
Tachycardia NOS	xx (xx.x)	xx (xx.x)	xx (xx.x)	xx (xx.x)	xx (xx.x)	xx (xx.x)

Numbers (n) represent counts of subjects.

A subject with multiple severity grades for an AE is only counted under the maximum grade.

MedDRA version <xx.x>, CTCAE version <x.xx>.

**Table 14.3.1-1.6 Adverse events leading to study drug discontinuation, regardless of study drug relationship by primary system organ class, preferred term, maximum severity and treatment group (Safety Set)**

Primary system organ class Preferred term	Cohort A (N=xxx)		Cohort B (N=xxx)		All Subjects (N=xxx)	
	All grades n (%)	Grade ≥3 n (%)	All grades n (%)	Grade ≥3 n (%)	All grades n (%)	Grade ≥3 n (%)
Number of subjects with at least one event	xx (xx.x)	xx (xx.x)	xx (xx.x)	xx (xx.x)	xx (xx.x)	xx (xx.x)
Cardiac disorders						
-Total	xx (xx.x)	xx (xx.x)	xx (xx.x)	xx (xx.x)	xx (xx.x)	xx (xx.x)
Angina pectoris	xx (xx.x)	xx (xx.x)	xx (xx.x)	xx (xx.x)	xx (xx.x)	xx (xx.x)
Oedema NOS	xx (xx.x)	xx (xx.x)	xx (xx.x)	xx (xx.x)	xx (xx.x)	xx (xx.x)
Oedema lower limb	xx (xx.x)	xx (xx.x)	xx (xx.x)	xx (xx.x)	xx (xx.x)	xx (xx.x)
Bradycardia NOS	xx (xx.x)	xx (xx.x)	xx (xx.x)	xx (xx.x)	xx (xx.x)	xx (xx.x)
Oedema peripheral	xx (xx.x)	xx (xx.x)	xx (xx.x)	xx (xx.x)	xx (xx.x)	xx (xx.x)
Sinus bradycardia	xx (xx.x)	xx (xx.x)	xx (xx.x)	xx (xx.x)	xx (xx.x)	xx (xx.x)
Tachycardia NOS	xx (xx.x)	xx (xx.x)	xx (xx.x)	xx (xx.x)	xx (xx.x)	xx (xx.x)

Numbers (n) represent counts of subjects.

A subject with multiple severity grades for an AE is only counted under the maximum grade.

MedDRA version <xx.x>, CTCAE version <x.xx>.

**Table 14.3.1-1.7 On-treatment deaths and serious adverse events by system organ class and preferred term (Safety Set)**

Primary system organ class Preferred term	Cohort A N=xxx n (%)	Cohort B N=xxx n (%)	All subjects N=xxx n (%)
Total number of subjects affected			
Subjects affected by serious adverse events / exposed (%)	xxx/xxx (xx.xx)	xxx/xxx (xx.xx)	xxx/xxx (xx.xx)
Number of deaths (all causes)	xx	xx	xx
Number of deaths resulting from adverse events*	xx	xx	xx
Infections and infestations			
Pneumonia			
Subjects affected / exposed (%)	xxx/xxx (xx.xx)	xxx/xxx (xx.xx)	xxx/xxx (xx.xx)
Occurrences causally related to treatment/all	xx/xx	xx/xx	xx/xx
Deaths causally related to treatment/all	xx/xx	xx/xx	xx/xx
Sepsis			
Subjects affected / exposed (%)	xxx/xxx (xx.xx)	xxx/xxx (xx.xx)	xxx/xxx (xx.xx)
Occurrences causally related to treatment/all	xx/xx	xx/xx	xx/xx
Deaths causally related to treatment/all	xx/xx	xx/xx	xx/xx
Investigations			
Platelet count decreased			
Subjects affected / exposed (%)	xxx/xxx (xx.xx)	xxx/xxx (xx.xx)	xxx/xxx (xx.xx)
Occurrences causally related to treatment/all	xx/xx	xx/xx	xx/xx
Deaths causally related to treatment/all	xx/xx	xx/xx	xx/xx
Weight decreased			
Subjects affected / exposed (%)	xxx/xxx (xx.xx)	xxx/xxx (xx.xx)	xxx/xxx (xx.xx)
Occurrences causally related to treatment/all	xx/xx	xx/xx	xx/xx
Deaths causally related to treatment/all	xx/xx	xx/xx	xx/xx

etc.

\*Number of deaths resulting from adverse events corresponds to deaths resulting from serious AE causally related to treatment.

Occurrences causally related to treatment/all: all occurrences are all SAEs occurrences regardless of causality to treatment.

Deaths causally related to treatment/all: all deaths are all SAEs with fatal outcome regardless of causality to treatment.

MedDRA version <xx.x>.

*Programming Note:*

*Sort system organ classes alphabetically; preferred terms in descending frequency in Investigational drug column of highest relevance and subgroup (e.g. subgroup with highest N).*

*Include only on-treatment events (as defined in SAP).*

*“Occurrences causally related to treatment/all”: all occurrences are all SAEs occurrences regardless of causality to treatment*

*“Deaths causally related to treatment/all”: all deaths are all SAEs with fatal outcome regardless of causality to treatment*

*Only subjects having at least one serious adverse event are considered.*

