#### **7.3.1.4. Disease-Related Events and/or Disease-Related Outcomes Not Qualifying as SAEs**

An event which is part of the natural course of the disease under study (i.e., disease progression or hospitalization due to disease progression) does not need to be reported as an SAE. Death due to disease under study is to be recorded on the Death eCRF form. However, if the underlying disease (i.e., progression) is greater than that which would normally be expected for the subject, or if the investigator considers that there was a causal relationship between treatment with study medication(s) or protocol design/procedures and the disease progression, then this must be reported as an SAE.

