### **On-treatment assessment/event and observation periods**

The overall observation period will be divided into three mutually exclusive segments:

**Pre-treatment period** is defined as from day of patient's informed consent to the day before first administration of study treatment

**On-treatment period** is defined as from date of first administration of study treatment to 30 days after date of last actual administration of study treatment (including start and stop date)

**Post-treatment period** is defined as starting at day 30+1 after last administration of study treatment.

Notes: if data on clock time is available in the clinical database (e.g. for time of blood/urine sample taken, ECG performed, etc. and first study treatment administration), a more precise distinction between pre-treatment and on-treatment periods is encouraged to be used. If dates are incomplete in a way that clear assignment to pre-, on-, post-treatment period cannot be made, then the respective data will be assigned to the on-treatment period.

Safety summaries (tables, figures) include data from the pre-treatment period (to display the baseline status e.g. for ECG) and the on-treatment period, i.e. data from the post-treatment period with the exception of deaths should not be included unless requested from Health Authorities or external committees.

In particular, summary tables for adverse events (AEs) will summarize only on-treatment events, with a start date during the on-treatment period, the so-called *treatment-emergent* AEs.

However, all safety data (including those from the post-treatment period) will be listed and those collected during the pre-treatment and post-treatment period are to be flagged.

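### The SAE-only programming note in SAP Table 14.3.1-1.7 exempts no row, so applied as written it would leave out of the all-cause death row any on-treatment death in a subject with no on-treatment SAE

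*SAP*

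**What the plan says.** The shell for Table 14.3.1-1.7 is titled "On-treatment deaths and serious adverse events by system organ class and preferred term (Safety Set"). Its header block has a row of subjects affected by SAEs over subjects exposed, a row "Number of deaths (all causes"), and a starred row for deaths resulting from adverse events. Two programming notes set what goes in. One fixes the period: "Include only on-treatment events (as defined in SAP"). The other fixes the subjects: "Only subjects having at least one serious adverse event are considered". Neither is tied to particular rows.

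SAP section 2.1.1 defines the on-treatment period as running "from date of first administration of study treatment to 30 days after date of last actual administration of study treatment".

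Protocol 7.3.1.4 deals with events that belong to the natural course of the disease. Its example is "disease progression or hospitalization due to disease progression) does not need to be reported as an SAE". It continues: "Death due to disease under study is to be recorded on the Death eCRF form". There is an exception: progression beyond what would be expected for the subject, or progression the investigator links causally to study medication or protocol procedures, must be reported as an SAE.

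The starred row carries its own footnote: "Number of deaths resulting from adverse events corresponds to deaths resulting from serious AE causally related to treatment".

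**The concern.** An all-cause death count should not depend on whether the subject also had an SAE. Here the note imposes that condition, and the protocol's reporting rule means that one foreseeable kind of death, from the melanoma itself, need not generate an SAE. The deaths exposed to omission are therefore those from the disease under study.

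What is at stake is a wrong number in one cell, and two tables in the same report giving different counts of on-treatment deaths for the same subjects. It deserves attention because the close-out report has no survival analysis: the SAP states under Last contact date that survival data will not be analysed. The death tables and the death listing are thus the study's only mortality output, and they should agree.

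**Working it through.** The plan states no figure to reproduce. The check sets the rules side by side and then applies them to a small count.

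**Rules compared**

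| Feature | Table 14.3.1-1.3 | Table 14.3.1-1.7, all-cause death row |
|---|---|---|
| Population | Safety Set | Safety Set |
| Period | On-treatment | On-treatment |
| SAE needed to be counted | No | Yes, if the note is applied as written |
| Deaths from disease progression | Own row | Only if the subject had an on-treatment SAE |

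Population and period match, so the SAE condition is the only thing that can make the two death counts differ.

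**Which deaths are lost.** A subject is dropped from the row only if all three of these hold:

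1. The death falls in the on-treatment period.
2. The death, or the progression behind it, was not reported as an SAE. Protocol 7.3.1.4 allows this for a death from melanoma unless its exception applies.
3. The subject had no other on-treatment SAE.

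A subject with any unrelated SAE stays in, as does one whose progression was reported under the exception.

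**Counts.** Let D be the number of on-treatment deaths and k the number of those in subjects with at least one on-treatment SAE.

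- Table 14.3.1-1.3 gives D.
- Table 14.3.1-1.7, with the note applied to every row, gives k.
- Deaths lost from the row = D − k.

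SAP section 3.1 gives 6 enrolled subjects. The documents give neither D nor k, so the values below are assumed to show scale, with all six taken to have been treated.

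| D | k | Table 14.3.1-1.3 | Table 14.3.1-1.7 | Lost (D − k) | Lost / 6 |
|---|---|---|---|---|---|
| 1 | 0 | 1 | 0 | 1 | 16.7% |
| 1 | 1 | 1 | 1 | 0 | 0.0% |
| 2 | 0 | 2 | 0 | 2 | 33.3% |
| 2 | 1 | 2 | 1 | 1 | 16.7% |
| 2 | 2 | 2 | 2 | 0 | 0.0% |

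The death rows of Table 14.3.1-1.7 print counts only, so the percentages are a guide to scale and would not appear there.

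**After the correction.** If the SAE condition is kept to the SAE numerators, the all-cause row becomes D and equals Table 14.3.1-1.3 in every line.

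**The case against.** The best answer is that the note was never meant for the death row. If it governed every cell, the row of subjects affected over subjects exposed would always read 100%, because the exposed would also be cut down to subjects with an SAE. A parallel sentence sits under Table 14.3.1-1.8 for non-serious events, again beside an exposed denominator, so it looks like template wording aimed at event rows. The table's title and the all-causes label point the same way.

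This is a good argument about intent, and it may well be right. It does not settle the matter, because the note names no rows. If some rows must be exempted for the table to make sense, the programmer is left to guess which. The title and label show what the row ought to contain; they support correcting the note.

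A second objection is that no death goes unreported. That stands. SAP 2.8.2 requires summaries of on-treatment deaths and of all deaths in the Safety Set, plus a listing of all deaths. Tables 12-6 and 14.3.1-1.3 have a disease-progression row and no SAE filter. A reader might infer that the report as a whole would understate mortality; the documents do not support that.

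A third concerns the starred row. A reader might infer that its restriction to treatment-related SAEs hides a fatal peri-operative SAE judged unrelated. It does not. The definition is printed in the footnote, the preferred-term rows show all fatal SAEs whatever their causality, and Table 12-2 has a fatal-SAE line separate from its treatment-related line. What remains is a label broader than its definition.

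**Conclusion.** The point holds, at small scale. As written, the note gives the wrong rule for the all-cause death row of Table 14.3.1-1.7. Any on-treatment death in a subject with no on-treatment SAE would be missing from that row, which could then conflict with Table 14.3.1-1.3. Each such death is 1 of 6 enrolled subjects (1/6 = 16.7%). The conclusion assumes that the note is applied literally and that such a death occurred; the documents do not say whether one did.

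Four stronger readings should be resisted:

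- **That melanoma deaths as a class drop out.** Only those in subjects with no on-treatment SAE of any kind would.
- **That the row should also match Table 14.3.1-1.4 and Listing 14.3.2-1.1.** The footnote to Table 14.3.1-1.4 takes in deaths more than 30 days after last treatment, and the listing takes in other deaths in the database. Those differ from an on-treatment count by design.
- **That the expected loss can be sized from historical survival.** Taking the protocol's median of 2.8 to 4 months, exponential survival and a window of 37 to 44 days (7 to 14 days of dosing plus 30), 1 − 0.5^(t/median) gives 19% to 30%. That estimates deaths of every kind, not deaths without an SAE. It also assumes dosing ends at surgery, whereas the protocol lets subjects with remaining disease resume treatment, which lengthens the window.
- **That a lost death is 1 in 5 of Cohort A.** This infers five subjects from the planned enrolment order; the cohort split of the six is not reported.

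**What to change.** In the programming note to Table 14.3.1-1.7, state that the restriction to subjects with at least one SAE applies only to the SAE numerator rows. State that the all-cause death row counts every on-treatment death in the Safety Set, including those recorded only on the Death eCRF. Add a check that this row equals the total in Table 14.3.1-1.3. As a minor wording change, relabel the starred row as deaths from treatment-related SAEs, to match its footnote.

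The cost is one edited programming note, one row label and one reconciliation check. No new data or analysis is needed.
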